6.6 Dose modification

Not applicable for the IMP.

6.6.1 Prohibited concomitant treatments (medications and therapies)

The following concomitant medications will be prohibited at screening visit (V1) and as concomitant medication to the IMP during the study ([Table 6-7](#)) with the exception of immunoglobulins which are allowed to be used concomitantly with DZP after randomization if medically indicated. In case one of these medications has to be initiated during the study the IMP needs to be permanently discontinued (with the exception of immunoglobulins).

The impact of initiation of prohibited medications on the study conduct should be discussed upfront, if possible, with the Medical Monitor and/or Sponsor's Study Physician.

Table 6-7: Prohibited medications and required wash-out periods prior to Screening (Visit 1)

Generic (trade) names	Wash-out period prior to Screening ^a	Generic (trade) names	Wash-out period prior to Screening
Biologics (mAbs and Fusion Proteins)		Immunosuppressants	
Abatacept (CTLA4-Ig) (Orencia [®])		High-dose cyclophosphamide (Cytoxan [®])	
Belimumab (Benlysta TM) (iv and sc)		Pimecrolimus (Elidel [®])	
Blisibimod		Sirolimus (Rapamune [®])	
Eculizumab (Soliris [®])		---	
ETI-201 (Elusys Heteropolymer Product)		Others	
Rituximab (Rituxan [®]), Ofatumumab (Arzerra [®]), Obinutuzimab (Gazyva [®]), Ocrelizumab, Veltuzumab		Intravenous immunoglobulin	
Natalizumab (Tysabri [®])		Rigerimod (Lupuzor TM)	
Vedolizumab (Entyvio [®])		Minocycline	
Tabalumab		Thalidomide or lenalidomide (Thalomid [®] , Revlimid [®])	
TACI-Ig (atacicept)		JAK inhibitors (eg, Baricitinib)	
Tocilizumab (Actemra [®] , MRA)		TYK 2 Inhibitors (eg, BMS-986165)	
BIIB059 (anti-BDCA2)		IFN kinoid	
Anifrolumab			
Sifalimumab (MEDI 545)			
Ustekinumab (Stelara)			

Table 6-7: Prohibited medications and required wash-out periods prior to Screening (Visit 1)

Generic (trade) names	Wash-out period prior to Screening ^a	Generic (trade) names	Wash-out period prior to Screening
Any other investigational drug or off-label drug used to treat SLE, cutaneous Lupus or [REDACTED] but not mentioned in this table	Contact Medical Monitor before using		

^a The wash-out period refers to the last administration of the relevant medication.

BDACA2=blood dendritic cell antigen 2; IFN=interferon; JAK=Janus kinase; mAbs=monoclonal antibodies;

MRA=myeloma receptor antibody; SLE=systemic lupus erythematosus; TYK 2=tyrosine kinase 2

Note: Topical formulations (eg, eye drops) are permitted without wash-out, unless otherwise indicated.

Vaccines

Administration of live vaccines should not occur during the conduct of the study. If a study participant receives a live vaccine, temporary or permanent discontinuation of study medication may be needed. In case of considered application of live vaccines the Medical Monitor and/or Sponsor's Study Physician should be contacted to discuss the impact on further study conduct.

Administration of non-live vaccines is allowed during the study at the discretion of the Investigator and should be documented. Local and international guidance on vaccination in immunocompromised patients (Furer et al, 2020; Van Assen et al, 2011; Murdaca et al 2016; Mason et al, 2021, ACR 2021, Geisen et al, 2021) should be considered.

According to local and international guidance approved SARS-CoV-2 vaccines are endorsed to be used in patients receiving immunosuppressant treatment (ACR 2021; EULAR 2021).

It cannot be excluded that the effectiveness of some vaccines may be compromised by DZP or any other concomitant immunosuppressant drug as part of standard of care. Therefore, blood samples will be collected to be able to determine the effect of DZP on the immune response to vaccines, eg, [REDACTED] as indicated.

The potential benefits and risks and vaccine administration options should be discussed with the study participant.

In case of administration of investigational Coronavirus Disease 2019 (COVID-19) vaccine (vaccines without regulatory authorization or emergency authorization) study medication should not be administered within 2 weeks after vaccination.

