20a. Study participants who have received live/live attenuated vaccines within 6 weeks prior to the first study medication infusion (Visit 2) or who plan to receive these vaccines during the study or up to 12 weeks after the final dose of study medication will be excluded. Use of nonlive vaccines is allowed during the study; however, based on current evidence, it cannot be excluded that the effectiveness of these vaccines may be compromised by the study medication. Investigator should consider local and international guidance on vaccination in immunosuppressed patients and discuss risks, benefits and administration options with participants (for more details see also Section 6.6.1 and Section 8.2.7).

Prior/Concomitant therapy

21. Study participant has active lupus that, in the opinion of the Investigator or according to local or international guidances, requires an increase in SOC therapy outside of that permitted in Section 6.5.1.

22. Study participants requiring plasma exchange or immunoabsorption in the 16 weeks prior to Visit 2 or at any time during the study.

23. Study participant has used the prohibited medications listed in [Table 6-7](#), regardless of route (with the exception of eye drops), within the time frame (Wash-Out Period) listed in the table prior to Screening (Visit 1). Study participant has used investigational agents not included in [Table 6-7](#), including other investigational or recently approved biologics, off-label use of immunomodulators, or device products, within 12 weeks or 5 times the half-life prior to Screening (Visit 1), whichever is longer. Concomitant participation in studies where no product or device is administered/used may be allowed if discussed and approved by the Medical Monitor/UCB. If there are any questions regarding acceptable wash-out periods not mentioned, the Investigator should contact the Medical Monitor.

24. Hormone replacement therapy is allowed provided it is not initiated within the 4 weeks prior to Screening (Visit 1) or during the study. The hormone replacement therapy may be decreased and/or discontinued at any time during the study.

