8.1.3 Derived endpoints

8.1.3.1 BILAG 2004-based Composite Lupus Assessment

A study participant is considered to be a BILAG 2004-based Composite Lupus Assessment (BICLA) responder if all of the following is fulfilled:

1. BILAG 2004 improvement without worsening, defined as BILAG 2004 Grade As at Baseline Visit improved to B/C/D, and BILAG 2004 Grade Bs at Baseline Visit improved to C/D, and no BILAG 2004 worsening in other BILAG 2004 organ systems (that had BILAG 2004 Grade C, D, or E at Baseline) such that there are no new BILAG 2004 Grades A nor greater than 1 new BILAG 2004 Grade(s) B; and
2. No worsening in the SLEDAI-2K total score compared to Baseline Visit (defined as no increase in SLEDAI-2K total score); and
3. No worsening in the PGA compared to Baseline Visit (“no worsening” is defined as either no worsening or worsening $<10\%$ of the full 100mm VAS, equivalent to less than a 10mm increase in the PGA compared to Baseline Visit (V2) score).

Escape treatment intervention as indicated by Investigator until the assessment time point will be defined as intercurrent event for the primary endpoint leading to non-response from the day after the event onward.

Escape treatment intervention is defined as:

1. Any dose increase or new start of systemic antimalarials or immunosuppressants from Screening Visit and during Treatment Period
2. Any increase in dose or new start of a moderate to high potency topical immunosuppressant (eg, Tacrolimus) used for an organ system with SLE disease activity during the study
3. Any increase of prednisone equivalent dose within the first 4 weeks (up to Week 4) that is above the Baseline level by $>50\%$ of the Baseline level or of $>10\text{mg/day}$, whichever is higher, which does not return to the Baseline level within 7 days after increase above Baseline level
4. Any increase of prednisone equivalent dose for a SLE indication above Baseline level after Week 4
5. Any increase of prednisone equivalent dose by $>50\%$ or 5mg/day , whichever is lower, for more than 1 day within 8 weeks prior to an assessment for any indication after Week 4.
6. More than 1 corticosteroid intra-articular injection up to Week 12
7. Any corticosteroid intra-articular injection after Week 12 for an SLE indication
8. Any intramuscular administration of corticosteroid for an SLE indication
9. Any iv administration of corticosteroid for an SLE indication

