If a treatment change represents an intercurrent event, it will be confirmed by a blinded independent adjudicator.

In addition, study participants who permanently discontinue study medication prematurely or are withdrawn from the study are categorized as non-responders for the primary analysis (see Section 9.3.1).

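### Immunoglobulin may be started for lupus after randomization without stopping study drug, and the protocol's escape-treatment definition does not name it, so such a participant can be scored a BICLA responder

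*Protocol*

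**What the plan says.** Protocol Section 6.6.1 prohibits the Table 6-7 drugs at Screening and alongside study drug, "with the exception of immunoglobulins which are allowed to be used concomitantly with DZP after randomization if medically indicated". If another listed drug has to be started, study drug must be stopped permanently; the same sentence repeats the immunoglobulin exception. Table 6-7 lists "Intravenous immunoglobulin" under 'Others', in a separate block from 'Immunosuppressants'.

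Protocol Section 8.1.3.1 defines escape treatment by nine items. Item 1 is "Any dose increase or new start of systemic antimalarials or immunosuppressants from Screening Visit and during Treatment Period". Item 2 covers topical immunosuppressants, and items 3 to 9 cover corticosteroids by dose, route and timing. For the primary endpoint, an escape intervention is an intercurrent event "leading to non-response from the day after the event onward". The same section adds that "study participants who permanently discontinue study medication prematurely or are withdrawn from the study are categorized as non-responders for the primary analysis". Section 9.6 repeats these rules and scores a missing response as non-response.

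Section 6.6.2 lists the medications that may be used as escape treatment: corticosteroids and seven named immunosuppressants. Immunoglobulin is not among them.

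On apheresis, exclusion criterion 22 in Section 5.2 covers "Study participants requiring plasma exchange or immunoabsorption in the 16 weeks prior to Visit 2 or at any time during the study".

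**The concern.** BICLA is scored with a composite strategy: a participant who needs added lupus therapy is a non-responder, so a response is meant to reflect randomized treatment on stable background care. For the drugs in Table 6-7 that principle is enforced indirectly. Starting one ends study drug, and ending study drug is non-response. The exemption in Section 6.6.1 removes that link for immunoglobulin, and nothing visible in Section 8.1.3.1 replaces it. The amendment history gives only a safety reason for the exemption, namely that giving it together with DZP raises no safety concern. That does not settle how its use should be treated in the efficacy estimand.

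At stake is the scoring of the primary endpoint. The Week 12 and Week 24 key secondaries use the same BICLA response. Their intercurrent-event handling is deferred to the SAP, where the heading of Escape Treatment Intervention 1 says it applies to landmark endpoints.

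**Working it through.** **1. Does any visible rule make an SLE-indicated immunoglobulin start a non-response?**

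| Route to non-response | Where | Triggered? |
|---|---|---|
| Permanent discontinuation after starting a Table 6-7 drug | Protocol 6.6.1, 8.1.3.1, 9.6 | No; immunoglobulin is exempted |
| Escape item 1, systemic antimalarials or immunosuppressants | Protocol 8.1.3.1 | Not named; Table 6-7 keeps the classes apart |
| Escape item 2, topical immunosuppressants | Protocol 8.1.3.1 | No |
| Escape items 3 to 9, corticosteroids | Protocol 8.1.3.1 | No, unless steroids are also raised or given as described |
| Study withdrawal or missing Week 48 response | Protocol 8.1.3.1, 9.6 | No |
| Blinded adjudication | Protocol 8.1.3.1 | Confirms whether a treatment change is an intercurrent event; no stated power to add drugs |

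No row clearly applies. The participant must still satisfy all of BICLA: every Baseline Grade A and B improved, no new A and at most one new B, no rise in SLEDAI-2K, and a PGA rise below 10 mm.

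**2. The plan's own power figure.** Inputs from Protocol Section 9.8 and SAP Section 2.4: 104 placebo and 208 DZP participants, response rates 0.32 and 0.52, two-sided 0.05, Fisher's exact test, stated power 90%. Exact enumeration gives 91.1%, so the figure reproduces to within about a point.

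**3. Effect of one case.** Scoring one participant as a responder instead of a non-responder shifts the arm's rate by 1/n:
- placebo: 1/104 = 0.96 percentage points
- DZP: 1/208 = 0.48 percentage points

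**4. Illustration.** The documents give no usage rate, so 0 to 5% per arm is assumed. Let uP and uD be the shares of placebo and DZP participants who start immunoglobulin for SLE. Take 0.32 and 0.52 as the rates with those participants scored as non-responders, and assume every one of them is instead counted a responder. Then

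difference = (0.52 + uD) − (0.32 + uP) = 0.20 + (uD − uP).

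| uP | uD | Difference | Fisher power |
|---|---|---|---|
| 0 | 0 | 0.20 | 91.1% |
| 2% | 2% | 0.20 | 90.9% |
| 5% | 5% | 0.20 | 90.6% |
| 2% | 1% | 0.19 | 87.7% |
| 5% | 2% | 0.17 | 79.1% |
| 5% | 0 | 0.15 | 68.1% |
| 2% | 5% | 0.23 | 96.7% |

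For scale, 2% of placebo is 0.02 × 104 ≈ 2 people and 5% is about 5; 5% of DZP is 0.05 × 208 ≈ 10. Each row overstates the shift for the use it assumes, because not every user would meet BICLA. Only the gap between arms moves the estimate; equal use leaves it at 0.20.

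**The case against.** The strongest objection is that the operative text cannot be read. Protocol Section 6.6.2 sends the detail of intercurrent-event handling to the SAP. Protocol Section 9.3.1, SAP Section 4.5.1 and the SAP's intercurrent-event table (Table 8-1) are all redacted, as is the rationale for SAP Amendment 3. The SAP may already name immunoglobulin. That stands, and it confines the point to the protocol's own definition, which is fully visible. The readable rows of SAP Table 3-1 show no change to the escape definition, but this does not settle what the redacted text says.

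Second, item 1 says immunosuppressants without a closed list, and the Appendix 13 rationale for exclusion 23 describes the prohibited drugs generally as immunosuppressive. Someone could therefore read item 1 to include immunoglobulin, although Table 6-7 separates the two. Section 7.1.3 also requires discontinuation for induction with an approved biological immune response modifier, pointing to Section 6.6, where immunoglobulin is exempted. If either text is meant to cover it, the passages must be reconciled. Two possible readings of a primary-endpoint rule are a reason to clarify it.

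Third, the documents never describe immunoglobulin as lupus rescue. The exemption speaks of medical indication, which may be unrelated to SLE, and steroids given for SLE alongside it would often trigger items 4, 8 or 9. SAP Section 6.5 also tabulates SLE-related concomitant medication by arm, so unequal use would be visible. These points limit the likely size but do not change how a case would be scored.

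Some stronger inferences are tempting and unsupported. Improvement in the treated organ system does not by itself make a responder, because all BICLA criteria must be met. The wash-out requirement does not show that the protocol regards immunoglobulin as effective in lupus, since the stated reason is immunosuppression and infection risk.

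**Conclusion.** The gap is real on the visible protocol text: an SLE-indicated immunoglobulin start triggers neither permanent discontinuation nor any named escape item, so a participant who otherwise meets BICLA can be scored a responder. Confidence is moderate, because the matching SAP text is redacted and item 1 could arguably be read to cover the drug.

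The effect is probably small. It is 0.96 points per placebo case and 0.48 points per DZP case, with frequency unknown. A reader might infer that the bias must run toward no difference, on the argument that poorly controlled placebo participants would receive more of it. That is plausible, but no usage data support it; more use on DZP would inflate the effect. The power figures above rest on assumed use and on every user becoming a responder, so they show sensitivity and are not a forecast. The planned sample size is unaffected. The point merits correction because it concerns the primary endpoint's scoring rule and is cheap to close before unblinding.

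**What to change.** Add one item to the escape-treatment definition in Protocol Section 8.1.3.1: *any new start of systemic immunoglobulin for an SLE indication after Baseline*. Score it like the other items, as non-response from the day after the event, with confirmation by the blinded independent adjudicator. A start for a non-SLE indication would not count. Check SAP Escape Treatment Intervention 1 and make it match; if it already covers this, only the protocol needs aligning.

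As a secondary point, score plasma exchange or immunoadsorption for SLE the same way. Exclusion 22 names their use during the study, but neither Section 7.1.3 nor Section 8.1.3.1 attaches a consequence to it.

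The cost is a line or two in the definition and in the adjudication instructions. No new data collection should be needed: SAP Section 6.5 says the CRF has an investigator tick box for SLE-relatedness of medications, and SAP Section 6.3 lists what each concomitant procedure relates to. Response rates may fall slightly. The change affects endpoint scoring only and takes no position on what care is permitted.

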6.6.2 Escape medication

Although the use of escape medications is allowed at any time of the study, it should be delayed, if possible, for at least 8 weeks following the first administration of study treatment. Data from Phase 1 and Phase 2 studies suggest that DZP has a fast onset of action however it can take several weeks until the potential therapeutic effect of DZP fully develops. Escape treatment should be initiated as clinically indicated by the Investigator or other qualified physicians

treating the participant. Investigators should discuss the impact of escape treatment use on study conduct with the Medical Monitor before initiation.

Initiation of escape treatment may be handled as intercurrent event in estimands, which will be detailed in the statistical analysis plan (SAP) as described in Section 9.3.1. For the primary endpoint, specification of how escape treatment will be handled as an intercurrent event is detailed in Section 8.1.3.1, Section 9.3.1, and Section 9.6.

The date and time of escape medication administration as well as the name and dosage regimen of the escape medication must be recorded.

In case of use of escape treatment the study medication does not have to be automatically discontinued, however if the escape treatment in combination with DZP represents a safety concern (see Section 6.6) for the study participant the study medication should be discontinued but the study participant should remain in the study under observation. Investigators are advised to contact the Medical Monitor upfront if possible, to discuss the potential impact on the further study conduct in case study medications should be permanently discontinued.

The following escape medications may be used as indicated:

- Corticosteroids (new initiation or increase in dose)
- Immunosuppressants (new initiation or increase in dose):
 - azathioprine
 - methotrexate
 - mycophenolate mofetil
 - tacrolimus
 - low dose cyclophosphamide
 - cyclosporine
 - voclosporin

6.7 Criteria for study hold or dosing stoppage

UCB will hold further dosing if the following criteria are met during the course of the study and following case review to confirm causality and seriousness and/or severity of reported events:

- If regulators request a study hold.

If the IDMC recommends a study hold, UCB will consider the study hold as outlined in the IDMC charter.

6.8 Treatment after the end of the study

Study participants who complete the 48-week Treatment Period may be eligible to participate in an OLE study.

7 DISCONTINUATION OF STUDY MEDICATION AND PARTICIPANT DISCONTINUATION/WITHDRAWAL

[figure not shown]
7.1 Discontinuation of study medication

Study participants who discontinue study medication will be encouraged to stay in the study under observation. They should continue to be followed for all regularly scheduled visits for safety and efficacy assessments.

7.1.1 Liver chemistry stopping criteria

Discontinuation of study treatment for abnormal liver function should be considered by the Investigator when a participant meets one of the conditions outlined in [Figure 7-1](#) or if the Investigator believes that it is in best interest of the participant.

Figure 7-1: Phase 3-4 Liver Chemistry Stopping Criteria and Increased Monitoring Algorithm

Abbreviations: ALT=alanine aminotransferase; AST=aspartate aminotransferase; INR=international normalized ratio; SAE=serious adverse event; ULN=upper limit of normal.

Specific assessments and follow up actions for potential drug-induced liver injury are provided in [Section 10.6](#).

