7.1.2 QTc stopping criteria

If a clinically significant finding is identified (including, but not limited to changes from Baseline in QT interval corrected using Fridericia's formula [QTcF]) after enrollment, the Investigator or qualified designee will determine if the participant can continue in the study and if any change in participant management is needed. This review of the electrocardiogram (ECG)

printed at the time of collection must be documented. Any new clinically relevant finding should be reported as an AE.

A participant who develops an ECG finding which meets the bulleted criterion based on the ECG readings after first study drug application will be withdrawn from study medication.

- QTcF >500 msec OR Uncorrected QT >600 msec

For participants with underlying bundle branch block, follow the discontinuation criteria listed below:

Baseline QTcF with Bundle Branch Block	Discontinuation QTcF Threshold with Bundle Branch Block
< 450 msec	> 500 msec
450 to 480 msec	≥ 530 msec

See the Schedule of Activities (Section 1.3) for data to be collected at the time of treatment discontinuation and follow-up and for any further evaluations that need to be completed.

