7.1.3 Permanent and temporary study drug discontinuation due to other reasons

Study participants must be permanently discontinued from study medication (but not necessarily from the study) if any of the following occurs:

1. Study participant experiences a thromboembolic event.
2. Study participant requires an induction therapy with cyclophosphamide for management of acute flare of [REDACTED] or other severe manifestation of SLE, in the opinion of the Investigator.
3. Study participant requires an induction of therapy with an approved biological immune response modifier or an investigational drug (see Section 6.6).
4. Potential drug-induced liver injury (pDILI) and related to study medication in the opinion of the Investigator, regulators, or the Sponsor. Discontinuation of study treatment for abnormal liver function should be considered by the Investigator when a participant meets one of the conditions outlined in Figure 7-1 or if the Investigator believes that it is in best interest of the participant.
5. Study participant has an anaphylactic reaction related to study medication (fulfilling Sampson criteria as described in Section 10.14).
6. Study participant develops an active TB or NTM (see Section 8.2.6.3).

Study participants may be temporarily discontinued from study medication (but not necessarily from the study) if any of the following occurs, but may be restarted. Consultation with the Medical Monitor is advised before restart:

1. Study medication will be stopped if the study participant develops a medical condition (or laboratory abnormality or ECG change) that, in the opinion of the Investigator, compromises the study participant's ability to proceed with study medication or compromises the study

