Routine Urinalysis	
 • Specific gravity • pH, glucose, protein, blood, ketones, bilirubin, urobilinogen, nitrite, leukocyte esterase by dipstick • Protein, albumin, and creatinine (for protein:creatinine ratio [mg/mmol] and albumin:creatinine [mg/mmol] ratios) • Microscopy of sediment for RBCs, RBC casts, WBCs, and WBC casts 						
Other Screening Tests	
 • Follicle-stimulating hormone and estradiol (as needed in women of non-childbearing potential only) • Serum or urine human chorionic gonadotropin (hCG) pregnancy test (as needed for women of childbearing potential)^b • Serology (hepatitis B surface antigen, hepatitis B core antibody, and hepatitis C virus antibody), plasma HIV antibody, and reflex testing • Tuberculosis test (IGRA): Quantiferon test 
All study-required laboratory assessments will be performed by a central laboratory.
						

Laboratory Assessments	Parameters
Additional assessments	

NOTES :

- ^a Details of liver chemistry stopping criteria and required actions and follow-up assessments after liver stopping or monitoring event are given in Section 10.6. All events of ALT $\geq 3 \times$ upper limit of normal (ULN) and bilirubin $\geq 2 \times$ ULN ($>35\%$ direct bilirubin) or ALT $\geq 3 \times$ ULN and international normalized ratio (INR) >1.5 , if INR measured, may indicate severe liver injury (possible Hy's Law) and must be reported as an SAE (excluding studies of hepatic impairment or cirrhosis).
- ^b Local urine testing will be standard for the protocol (for all assessments after Screening) unless serum testing is required by local regulation or IRB/IEC.

Investigators must document their review of each laboratory safety report.

Laboratory results that could unblind the study will not be reported to investigative sites or other blinded personnel until the study has been unblinded.

10.3 Appendix 3: AEs – definitions and procedures for recording, evaluating, follow-up, and reporting

Definition of AE

AE Definition

• An AE is any untoward medical occurrence in a patient or clinical study participant, temporally associated with the use of study medication, whether or not considered related to the study medication.• NOTE: An AE can therefore be any unfavorable and unintended sign (including an abnormal laboratory finding), symptom, or disease (new or exacerbated) temporally associated with the use of study medication.

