10.6 Appendix 6: Liver safety – suggested actions and follow-up assessments

Participants with potential drug-induced liver injury must be assessed to determine if study medication must be discontinued. In addition, all concomitant medications and herbal supplements that are not medically necessary should also be discontinued.

Investigators should attempt to obtain information on study participants in the case of study medication discontinuation to complete the final evaluation.

Study participants with potential drug-induced liver injury should not be withdrawn from the study until investigation and monitoring are complete. All results of these evaluations and observations, as well as the reason(s) for study medication discontinuation and/or participant withdrawal (if applicable), must be recorded in the source documents. The eCRF must document the primary reason for discontinuation of study medication.

A specific monitoring plan must be agreed between the UCB study physician and the Investigator for study participants who have ALT >5 ULN. The monitoring plan should include any necessary follow-up assessments (until resolution of the abnormal lab values).

Table 10-1: Phase 3-4 liver chemistry stopping criteria and follow-up assessments

Liver Chemistry Stopping Criteria	
ALT-absolute	ALT \geq 8xULN
ALT Increase	ALT \geq 5xULN but $<$ 8xULN persists for \geq 2 weeks ALT \geq 3xULN but $<$ 5xULN persists for \geq 4 weeks
Bilirubin^{a,b}	ALT \geq 3xULN and bilirubin \geq 2xULN ($>$ 35% direct bilirubin)
INR^b	ALT \geq 3xULN and international normalized ratio (INR) $>$ 1.5, if INR measured
Cannot Monitor	ALT \geq 5xULN but $<$ 8xULN and cannot be monitored weekly for \geq 2 weeks ALT \geq 3xULN but $<$ 5xULN and cannot be monitored weekly for \geq 4 weeks
Symptomatic^c	ALT \geq 3xULN associated with symptoms (new or worsening) believed to be related to liver injury or [REDACTED]
Suggested Actions and Follow up Assessments	
Actions	

• Immediately discontinue study medication.• Report the event to the UCB within 24 hours.• Complete the liver event case report form (eCRF), and complete a serious adverse event (SAE) data collection tool if the event also met the criteria for an SAE.^b• Perform liver chemistry follow-up assessments.	
Follow Up Assessments	

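### When a liver stopping criterion is met, the protocol does not say consistently whether dosing must stop

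*Protocol*

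**What the plan says.** Five places in the protocol tell a site what to do with dosing when a liver criterion is met.

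- **Section 7.1.1:** "Discontinuation of study treatment for abnormal liver function should be considered by the Investigator when a participant meets one of the conditions" in Figure 7-1, or when the Investigator thinks stopping is in the participant's interest.
- **Section 7.1.3, permanent list, item 4:** the list is mandatory. The item's trigger is "Potential drug-induced liver injury (pDILI) and related to study medication in the opinion of the Investigator, regulators, or the Sponsor". Its second sentence then repeats the discretionary wording of 7.1.1.
- **Section 10.6:** the title speaks of "suggested actions and follow-up assessments", and the action block of Table 10-1 is headed the same way. The opening paragraph makes an assessment compulsory and lets the stop depend on its outcome. The first listed action is "Immediately discontinue study medication". A later action forbids restart without sponsor approval.
- **Table 10-1 footnote a:** if bilirubin cannot be fractionated at once, drug is to be discontinued at ALT at least 3xULN with bilirubin at least 2xULN. No discretion is mentioned.
- **Section 10.2 (Appendix 2), note a:** "Details of liver chemistry stopping criteria and required actions and follow-up assessments after liver stopping or monitoring event are given in Section 10.6".

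The temporary list in 7.1.3 has no liver-specific entry. Its item 1 begins "Study medication will be stopped if the study participant develops a medical condition (or laboratory abnormality or ECG change", but it applies only where the Investigator judges that safety or the ability to continue is compromised.

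**The concern.** The same laboratory result can lead to different dosing decisions depending on which section the site opens. The case that matters most is ALT at least 3xULN with bilirubin at least 2xULN, which the protocol itself labels as possible Hy's Law. Under 7.1.1 an Investigator may consider stopping and then decide to continue. Under Table 10-1 the drug stops at once.

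The kind of stop also matters. Section 8.1.3.1 counts permanent discontinuation as non-response but does not count a temporary hold. SAP Section 10.1 tabulates adverse events leading to temporary and to permanent stops separately. The protocol should therefore say whether meeting a criterion produces a hold, a permanent stop or neither.

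**Working it through.** **Step 1. Set the instructions side by side** for one event: a Table 10-1 criterion is met.

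| Place | Does dosing stop? |
|---|---|
| 7.1.1 | Investigator considers it |
| 7.1.3 item 4, first sentence | Yes, permanently, if judged drug-related |
| 7.1.3 item 4, second sentence | Investigator considers it |
| 10.6 opening | Depends on a compulsory assessment |
| Table 10-1 actions | Yes, immediately, but labelled suggested |
| Table 10-1 footnote a | Yes |
| Appendix 2 note a | The 10.6 actions are required |

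An Investigator who considers stopping and continues has complied with 7.1.1 and has not complied with Table 10-1 read through Appendix 2.

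**Step 2. Look for a reading that reconciles them.** One exists: hold at once, assess, then either restart with sponsor approval or stop permanently if the injury is judged drug-related. The opening of 10.6 and the restart clause both point this way, since a restart presumes a stop. What is missing is any statement that the hold is mandatory, or that 7.1.1 concerns only the permanent decision. The temporary list in 7.1.3, where such a hold belongs, does not contain it.

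**Step 3. Compare with the adjacent rule.** Section 7.1.2 says that a participant with an ECG finding "which meets the bulleted criterion based on the ECG readings after first study drug application will be withdrawn from study medication". Liver and QTc rules need not share a format, but the comparison shows that the protocol can state a binding stop when it intends one.

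**Step 4. Check what a binding hold would do to participants admitted with SLE hepatitis.** Exclusion 29a lets in ALT at or above 3xULN when it is ascribed to SLE hepatitis. Table 10-1 uses fixed ULN multiples: 3 to 5xULN for at least 4 weeks (28 days), and 5 to 8xULN for at least 2 weeks. With no Day 0, the time from Day -k to Day d is d + k - 1 days.

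- Screening on Day -1 to nominal Week 4: 28 + 1 - 1 = 28 days.
- Screening on Day -14 to nominal Week 4: 28 + 14 - 1 = 41 days.
- First dose (Day 1) to Day 28: 27 days. To Days 29, 30 and 31, still inside the visit window: 28, 29 and 30 days.

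If ALT is stable at 3 to 5xULN and the clock runs from Screening, the 4-week row is met at nominal Week 4. This assumes ALT is drawn at Screening and Week 4; the laboratory rows of the schedule are not legible. Today the Investigator's discretion absorbs this case. A mandatory hold would remove that discretion, so the fix needs an exception for it.

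**Step 5. Size per participant.** One changed Week 48 status moves an arm's response rate by 1/208 = 0.48 points (DZP) or 1/104 = 0.96 points (placebo), against a planned difference of 20 points. The wording is the same for both arms, and nothing in the documents gives the number of participants affected.

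**The case against.** The strongest reply is that this is editorial. Figure 7-1 is titled as an algorithm, cannot be seen here, and may state the action. The opening of 10.6 already links assessment to the stop, and the restart clause completes a workable sequence. Appendix 2 note a is a cross-reference under a laboratory table, not a dosing rule. For the bilirubin row, chemistry is repeated within 24 hours, the event is reported as an SAE, specialist advice is recommended, safety concerns go to the Medical Monitor immediately, and infusions are 4 weeks apart.

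Much of this stands, and it is why the point is minor. It does not remove the conflict. Sections 7.1.1 and 7.1.3 both introduce Figure 7-1 with the discretionary wording, so nothing in the figure can make that text binding. The controls bring the event to attention quickly but leave the stop to judgement where Table 10-1 says it is immediate.

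A reader might go further and infer that Table 10-1 automatically stops drug in participants admitted with stable SLE hepatitis, some of them already at Baseline. The documents do not support that. Under current wording a stop follows only if the discretionary language is ignored. The persistence rows are labelled as an increase. Before the first infusion there is no dosing to stop. Section 10.6 requires a monitoring plan agreed with the sponsor's physician for ALT above 5xULN, exclusion 29a requires a Medical Monitor discussion of eligibility, and exclusion 1 covers life-threatening conditions.

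**Conclusion.** The protocol gives inconsistent instructions on whether dosing stops when a liver criterion is met. An immediate hold followed by a decision on permanence is the likely intent, but no legible passage states it. A site could therefore redose at ALT at least 3xULN with bilirubin at least 2xULN while complying with 7.1.1.

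This is a minor safety-conduct point that should be corrected because correction is cheap. It rests on the legible text, with Figure 7-1 unseen. A reader might infer that the primary comparison is biased through discontinuations counted as non-response. The documents do not support that: the number affected cannot be derived, the wording is common to both arms, and no direction can be predicted.

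**What to change.** 1. **Section 7.1.1:** replace the discretionary sentence with *Study medication must be withheld when a stopping criterion in Figure 7-1 or Table 10-1 is met, pending the Section 10.6 assessment; restart only with sponsor approval.*
2. **Section 7.1.3:** in item 4 keep only the permanent stop for potential drug-induced liver injury judged related to study medication. Add the hold to the temporary list with its own *must*, because that list's lead-in is permissive.
3. **Table 10-1 and footnote a:** change discontinue to withhold. Mark the hold, 24-hour reporting and repeat liver chemistry as required, and leave the rest of the work-up as suggested. Align Appendix 2 note a and Figure 7-1.
4. **Narrow exception for participants admitted under the SLE-hepatitis clause of 29a:** the two ALT persistence rows (3 to 5xULN and 5 to 8xULN) do not trigger an automatic hold if ALT has not risen from the latest available pre-dose value and continued dosing is agreed with the Medical Monitor and documented. The rows for ALT at least 8xULN, bilirubin, INR and symptoms apply unchanged. The exception covers only the persistence rows, so the rows for ALT that "8xULN and cannot be monitored weekly for" the stated period also stay as they are.

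The cost is wording in one amendment or site letter. No new test is added; the three required actions are already listed in Table 10-1. Investigators lose the discretion to dose during the assessment, and an infusion may be delayed or missed. The hold is reversible and does not by itself count as non-response.
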